7.3.3 Assessment of Seriousness

Event seriousness will be determined according to the protocol definition of an SAE.

Event severity will be graded using the DAIDS toxicity table
<https://rsc.niaid.nih.gov/sites/default/files/daidsgradingcorrectedv21.pdf>

7.3.4 Assessment of Association

The association assessment categories that will be used for this study are:

- **Associated** – The event is temporally related to the administration of the study product and no other etiology explains the event.
- **Not Associated** – The event is temporally independent of the study product and/or the event appears to be explained by another etiology.

The investigator must provide an assessment of association or relationship of AEs to the study product based on:

- Temporal relationship of the event to the administration of study product
- Whether an alternative etiology has been identified
- Biological plausibility
- Existing therapy and/or concomitant medications.

7.4 Safety Oversight

7.4.1 Monitoring Plan

All AE and SAE will be reviewed by protocol team weekly, or more often if needed.

We will develop an independent Safety Monitoring Committee (SMC) or Data Safety Monitoring Board (DSMB) prior to the initiation of the study. We expect to recruit independent experts in **infectious disease medicine, pulmonary medicine, emergency medicine and biostatistics without conflicts of interest**. Primary safety endpoints will be developed in collaboration with the study sponsor and reviewed with the SMC/DSMB before the study is initiated. The SMC/DSMB will first meet after the first 5 participants have completed 16 weeks of observation. The SMC or DSMB will meet quarterly during the study and at approximately 2 to 4 weeks after the last person's follow-up are completed. The members of the SMC will be independent of the study team and free of any conflict of interest with the investigation and the sponsors. In order to monitor study participants for potential adverse events, the study coordinator will perform telephone symptom/adverse event visits on Days 2, 3, 4, 7, 9, and 11, in addition to the in-person monitoring on Days 5, 15, and 31 (see Table 1 Schedule of Events). This is particularly important for Days 6-14 during which there are no scheduled in-person study visits after completion of the study treatment. Study staff will call the participant on these days to verify their symptoms and evaluate for any adverse events that need to be reported to the study investigators.

7.5 Study compliance with clinical trial requirements

Study will be conducted in accordance with GCP and ICH. Specifically, regular QC will be conducted to document the following:

- There is documentation of the informed consent process and signed informed consent documents for each participant
- There is compliance with recording requirements for data points
- All SAEs are reported as required
- Individual participant study records and source documents align
- Investigators are in compliance with the protocol
- Regulatory requirements as per Office for Human Research Protections (OHRP), FDA, and applicable guidelines (ICH-GCP) are being followed.

8.1 Criteria for Discontinuation of the Study

Two cohorts of participants (N=30 each) will be sequentially enrolled and receive disulfiram daily for five days at doses of 1000mg or 2000mg. The independent Safety Monitoring Committee will review the safety and tolerability data after the first cohort has completed dosing and determine whether it is safe to proceed with enrolling the final cohort using the below criteria.

In addition, the study enrollment and dosing will be stopped and an ad hoc review by the SMC will be performed if any of the specific following events occur or, if in the judgment of the study physician, participant safety is at risk of being compromised:

- a. Death within one hour of drug administration
- b. Occurrence of a life-threatening allergic/hypersensitivity reaction (anaphylaxis), manifested by bronchospasm with or without urticaria or angioedema requiring hemodynamic support with pressor medications or mechanical ventilation, TRALI, TACO.
- c. One participant with an SAE associated with study product.
- d. Two participants with a Grade 3 or higher lab toxicity for the same parameter associated with study product. (Grading will be assessed using DAIDS Toxicity Table <https://rsc.niaid.nih.gov/sites/default/files/daidsgradingcorrectedv21.pdf>)
- e. An overall pattern of symptomatic, clinical, or laboratory events that the SMC considers associated with study product and that may appear minor in terms of individual events but that collectively may represent a serious potential concern for safety.
- f. Any other event(s) which is considered to be a serious adverse event in the good clinical judgment of the responsible physician. This will be appropriately documented.

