- Current use of oral lopinavir/ritonavir solution (and the inability to switch to a solid dosage form during the entire duration of the study).
- Current use of warfarin.
- ALT or AST > 2 x the upper limit of normal or total bilirubin outside the normal range.

	
 • Creatinine clearance (CrCl) < 50 mL/min by Cockcroft-Gault. • Allergy to rubber or thiuram derivatives
TEST PRODUCT, DOSE, AND ROUTE OF ADMINISTRATION	
Oral disulfiram given as 1000 mg daily (cohort 1) or 2000 mg daily (cohort 2) versus placebo for 5 consecutive days in adults with early symptomatic SARS-CoV-2 infection will be administered in a double-blind fashion.
 
Placebo tablets will be administered in a double-blind fashion and given as a single oral administration on days 1-5.

DURATION OF PARTICIPATION AND DURATION OF STUDY	
Study products will be administered at days 1-5. Participants will be observed on study at days 5, 15, and 31.
 
Participants will be randomized to either of two treatment arms, oral disulfiram or placebo.
 
Screening: up to 7 days prior to treatment randomization.
 
Treatment (for each arm): 5 days (participants to be observed for a total of 4 hours on the last treatment day, Day 5)
 
Follow-up (for each arm): 31 days after the initial dose for that treatment arm.
 
The total duration of the study is expected to be 31 days (approximately 1 month).

CONCOMITANT MEDICATIONS	
The following medications are not allowed during the study because of potential interactions with disulfiram: warfarin; any over the counter drug, food or other product that contains or might contain alcohol; if HIV-positive, specific protease inhibitor preparations (oral amprenavir solution, ritonavir solution, lopinavir/ritonavir solution, soft gelatin form of ritonavir or lopinavir/ritonavir, tipranavir).

EFFICACY EVALUATIONS	
 • Change in plasma inflammatory biomarker levels² • Change in SARS-CoV-2 viral load⁴ • Change in COVID-19 symptom severity³ (5-point scale)
PRIMARY ENDPOINTS	
 • Change in plasma inflammatory biomarker levels² (e.g., IL-6, IL-1β) at days 5, 15, and 31.

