SECONDARY ENDPOINTS	
 • Safety and tolerability • Change in SARS-CoV-2 PCR quantitative viral load⁴ at days 5, 15, and 31. • Change in COVID-19 clinical stage (five-point symptom severity scale³) at days 5, 15, and 31. • Time to recovery (date of symptom onset to date of complete resolution of symptoms) • If applicable, the proportion of participants hospitalized at day 5, 15, and 31. • If applicable, the proportion of participant deaths at day 5, 15, and 31
OTHER EVALUATIONS	
 • SARS-CoV-2 specific T- and B- cell responses⁵ • Pyroptosis (aberrant proinflammatory cell death) assay⁶ • High sensitivity SARS-CoV-2 antibody titer (IgM, IgE, IgA, IgG1, IgG2, IgG3, IgG4) • Changes in host gene and protein expression from matched blood and respiratory (NP) samples at the single cell level (B, T, natural killer, and myeloid cells). • Changes in T- and B-cell receptor (TCR/BCR) repertoire from matched blood and respiratory (nasal/oropharyngeal) samples.
SAFETY EVALUATIONS	All participants will be followed for possible adverse events (AEs) throughout their involvement in the study.
PLANNED INTERIM ANALYSES	A Safety Monitoring Committee (SMC) will be convened and will meet biannually to review all adverse events and the conduct of the study. Serious adverse events will be monitored by the committee on an ongoing basis throughout the study. All main analyses will be conducted on an intention-to-treat basis. Models will assess the relationship between the timing of disulfiram treatment initiation relative to symptom onset and study outcomes for key efficacy/activity endpoints. Stratified analyses will be performed based on symptom severity, as well as laboratory values (e.g., hs-CRP, ferritin, D-dimer levels at baseline).

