5.5.3 Study Drug/ Placebo Administration (Day 2)

Participant will come to the clinic for clinical laboratory to include complete blood count with differential, urea, electrolytes, creatinine, calcium, magnesium, phosphate, liver function tests, erythrocyte sedimentation rate (ESR), high sensitivity C-reactive protein (hs-CRP), D-dimer, lactate dehydrogenase (LDH), and ferritin, plasma PK testing, and Nasopharyngeal swab for SARS-CoV-2 viral load. Saliva for host DNA sequencing and potential future SARS-CoV-2 quantification (RNA levels and anti-SARS-CoV-2 IgA) will be collected.

The participant will be asked to hold the day 2 study medication until after the blood draw. After the blood has been collected, the participant will be asked to take their day 2 dose of study medication. The time of pre-dose blood draw and the study medication administration date and time will be recorded.

The subject will complete a daily symptom check using the COVID-19 symptom severity questions adapted from the Somatic Symptom Scale (SSS-8) (table 3) while at the clinic and will be assessed for any adverse events.

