5.5.6 Study Drug/ Placebo Administration (Day 5)

5.5.4.1 Pre-Dose (Hour -0.5 to Hour 0)

1. Questionnaire Evaluation
2. Targeted physical exam and vital signs
3. Clinical lab collection to include;
complete blood count with differential, urea, electrolytes, creatinine, calcium, magnesium, phosphate, liver function tests, erythrocyte sedimentation rate (ESR), high sensitivity C-reactive protein (hs-CRP), D-dimer, lactate dehydrogenase (LDH), and ferritin.
4. Samples collected for research (storage)
 - a. Blood: PBMC (CyTOF, single cell sequencing), plasma (plasma SARS-CoV-2 viral load), serum (SARS-CoV-2 serology)
 - b. Nasopharyngeal swab for SARS-CoV-2 viral load
 - c. Saliva for host DNA sequencing and potential future SARS-CoV-2 quantification (RNA levels and anti-SARS-CoV-2 IgA)

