5.5.9 Symptom/Adverse Event Telephone Follow-Up (Day 11)

Participant will self-administer a daily symptom/adverse event diary. Study coordinator will call patient to verify their symptoms and evaluate for any adverse events. If any AEs are reported, an AE form will be completed by the study coordinator, and the PI will be notified for any Grade 3 or above AE.

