5.5.10 Follow-Up (Day 15)

1. Questionnaire Evaluation
2. Targeted physical exam and vital signs
3. Clinical lab collection
 - a. Complete blood count with differential, urea, electrolytes, creatinine, calcium, magnesium, phosphate, liver function tests, erythrocyte sedimentation rate (ESR), high sensitivity C-reactive protein (hs-CRP), D-dimer, lactate dehydrogenase (LDH), and ferritin.
4. Samples collected for research (storage)
 - a. Blood: PBMC (CyTOF, single cell sequencing), plasma (plasma SARS-CoV-2 viral load), serum (SARS-CoV-2 serology)
 - b. Nasopharyngeal swab for SARS-CoV-2 viral load
 - c. Saliva for host DNA sequencing and potential future SARS-CoV-2 quantification (RNA levels and anti-SARS-CoV-2 IgA)

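### The review that opens the 2000 mg cohort has no data cut, so it may precede any safety lab after dose 5 in the latest cohort 1 enrollees; separately, the SMC meeting schedule needs correcting

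*Combined protocol and SAP*

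**What the plan says.** **The gate.** Section 8.1 asks the SMC to review the "safety and tolerability data after the first cohort has completed dosing and determine whether it is safe to proceed" with the second cohort, using the criteria listed below that sentence. The synopsis (Study Design) and Section 5.3.4 add only that safety criteria must be met. None of these names a follow-up day, a visit or a data cut-off.

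**Safety labs around dosing.**
- Day 2: Section 5.5.3 places the labs before the second dose: "The participant will be asked to hold the day 2 study medication until after the blood draw". The schedule of evaluations in Section 5.4 marks them as post-dose. The difference does not affect what follows.
- Day 5: both the schedule and Section 5.5.6 place the safety panel before dose 5, so it reflects four doses. The draws 2 and 4 hours after dose 5 are stored research and PK samples, with no safety panel.
- Day 15: the next safety panel, listed in Section 5.5.10 as "Complete blood count with differential, urea, electrolytes, creatinine, calcium, magnesium, phosphate, liver function tests" plus the inflammatory markers.

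**Clinical checks after dose 5.** The synopsis requires 4 hours of observation on Day 5. The schedule has vital signs at 2 and 4 hours and a symptom and adverse event check at 2 hours. Calls follow on Days 7, 9 and 11 (Sections 5.5.7 to 5.5.9). The next examination is on Day 15, and Section 7.4.1 confirms that no in-person visit is scheduled on Days 6 to 14.

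**SMC meetings.** In the synopsis (Planned Interim Analyses) the committee "will be convened and will meet biannually to review all adverse events and the conduct of the study". Section 7.4.1 says quarterly, and adds: "The SMC/DSMB will first meet after the first 5 participants have completed 16 weeks of observation". The synopsis gives participation as 31 days.

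**The concern.** This is the trial's only dose-escalation decision. Criterion (d) in Section 8.1 rests on laboratory toxicity, and criterion (e) partly does. At the earliest moment the text allows, both could be applied to the latest enrollees on the basis of labs taken after four of five doses.

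The protocol's own background gives reasons to want the later data. Section 4.1.6 reports 90% elimination of disulfiram in 3 days and a 22.1-hour half-life for one metabolite, so exposure outlasts the last dose. Section 7.1.1 lists hepatotoxicity among the known effects. Table 1 gives a median parent-drug AUC of 8,386 at 1000 mg and 22,331 at 2000 mg, a ratio of 22,331/8,386 = 2.7 for a doubling of dose. The documented concern at 2000 mg is neurological, seen in two participants who also received vorinostat (Sections 4.1.5 and 4.1.8). Such events would be found clinically, so the calls and the Day 15 examination matter as well as the labs.

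If toxicity first appeared after the Day 5 pre-dose draw in late cohort 1 enrollees, it could be recognized after some cohort 2 participants had started 2000 mg.

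**Working it through.** The plan gives no figure to reproduce here. The check is date arithmetic on the visit schedule.

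**Inputs.** Cohort 1 has 30 participants, 20 active and 10 placebo (Section 5.3.4). The last dose is on Day 5 and the next safety lab on Day 15, a gap of 10 days. The documents give no accrual rate for this trial, so 0.3 to 1.0 per day is assumed. The middle value, 13/21 = 0.62 per day, is the pace of the separate pilot cohort in Section 4.1.10.

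**Participants without a safety lab after dose 5.** Take enrolment as evenly spaced at r per day, and let the SMC decide d days after the last participant's Day 5. The participant enrolled k places before the last (k = 0 to 29) has no Day 15 lab if k/r < 10 − d. Calls are counted in the same way, with 6 days (Day 11) or 2 days (Day 7) in place of 10.

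| | r = 0.3 | r = 0.62 | r = 1.0 |
|---|---|---|---|
| No safety lab after dose 5, d = 0 | 3 | 7 | 10 |
| of these on active drug (× 2/3) | 2 | about 5 | about 7 |
| Same, d = 5 | 2 | 4 | 5 |
| Same, d = 10 | 0 | 0 | 0 |
| Day 11 call not yet made, d = 0 | 2 | 4 | 6 |
| Day 7 call not yet made, d = 0 | 1 | 2 | 2 |

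For example, at r = 0.62 and d = 0, k < 6.2 gives k = 0 to 6, which is 7 people. At one enrollee per week (r = 1/7), k < 1.43 gives 2. If cohort 2 opened at once at the same rate, the same counts (3, 7 and 10) bound the number who could be randomized to it before the last cohort 1 Day 15 lab.

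**First SMC meeting as written.** 16 × 7 = 112 days, which is 112 − 31 = 81 days longer than any participant is observed. The condition cannot be met.

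**First SMC meeting read as elapsed time.** Count days from the first participant's Day 1. The fifth participant starts at 4/r, so the meeting falls at 4/r + 112. The last cohort 1 Day 15 falls at 29/r + 14. The meeting follows the last Day 15 by 98 − 25/r days.
- r = 0.3: 98 − 83.3 = 14.7 days.
- r = 0.62: 98 − 40.3 = 57.7 days.
- r = 1.0: 98 − 25 = 73 days.
- The difference is zero at r = 25/98 = 0.255 per day, about 1.8 per week.
- At one per week the meeting is on day 28 + 112 = 140. The last Day 5 is then on day 203 + 4 = 207 and the last Day 15 on day 203 + 14 = 217, so that meeting could not be the escalation review. A quarterly meeting about 91 days later, near day 231, would follow the last Day 15 labs.

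**The case against.** The strongest reply is that nothing in Section 8.1 makes the SMC decide early. The review comes after dosing is complete, and a prudent committee can wait. An independent committee that receives data, meets and decides on the very day of the last fifth dose is unlikely, so the d = 0 counts are ceilings. Cohort 2 already depends on the SMC's determination. The stopping criteria (a) to (f) apply throughout, and the team reviews adverse events weekly. The earlier escalation trial reported no Grade 2 to 4 events, although its dosing is given as 3 days in Section 4.1.5 and 5 days in Section 4.1.8. All of this stands, and it limits the point to an under-specified gate with a modest effect. It does not supply the missing data cut.

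A reader might infer several stronger things that the documents do not support:
- **That there would be no safety information after dose 5.** Day 5 vital signs at 2 and 4 hours and the adverse event check would be available for everyone who attended, and research and PK blood is drawn. Only a safety panel and the later calls and examination would be missing.
- **That late toxicity would escape notice.** The Day 15 visit, calls and stopping rules still operate after cohort 2 opens.
- **That the whole SMC timetable is unworkable.** Quarterly or biannual meetings are each feasible. Only the 16-week condition is impossible.
- **That the timetable forces an early decision.** Read as elapsed time, the first meeting leaves no gap anywhere in the assumed accrual range. But Section 7.4.1 does not tie its meetings to escalation, so it settles the timing in neither direction.

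The meeting-schedule conflict is also a separate drafting error. It should be judged on its own and not used to add weight to the gate-timing point.

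**Conclusion.** The point holds in limited form. Section 8.1 can be satisfied while the latest cohort 1 enrollees have no safety lab after dose 5 and have not had their later calls. The number affected is at most 3 to 10 of 30 (about 2 to 7 on active drug), assuming evenly spaced accrual of 0.3 to 1.0 per day and a same-day decision. It falls to 2 to 5 with a 5-day lag and to none at 10 days. The consequence is delayed recognition of toxicity that first appears after the Day 5 pre-dose draw. No harm is predicted. A stated cut is a low-cost precaution and should be added.

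Separately, the 16-week trigger for the first SMC meeting cannot occur with 31-day follow-up, and the synopsis and Section 7.4.1 disagree on meeting frequency. Both need correcting whatever is decided about the gate.

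**What to change.** In Section 8.1, state that the SMC escalation review takes place once every cohort 1 participant still in follow-up has completed the Day 15 visit and the resulting safety labs are available, and that no one is randomized to cohort 2 until the SMC's decision is documented. Refer to this review in the synopsis (Study Design) and Section 5.3.4.

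Replace the meeting statements in the synopsis and Section 7.4.1 with one achievable schedule. An example: a first meeting after the first 5 participants complete Day 31, the escalation review above, ad hoc reviews under criteria (a) to (f), and a final meeting 2 to 4 weeks after last follow-up.

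The cost is a pause of about 10 days between cohorts, with no added visits, samples or participants. Eligibility requires symptom onset within 14 days and a positive test within 7 days, so some patients who present during the pause may pass those windows. At 0.62 per day about 6 would present (0.62 × 10 = 6.2), and not all of them would be lost.

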5.3.3 Participant Withdrawal

Participants can terminate study participation and/or withdraw consent at any time without prejudice. Randomized participants who withdraw from the study will not be replaced. If a participant discontinues study dosing (for example, as a result of an AE), every attempt should be made to keep the participant in the study and continue to perform the required study-related follow-up and procedures (see Section 8.1, Criteria for Discontinuation of Study Treatment). The investigator may withdraw participants if they are non-compliant with study procedures or if the investigator determines that continued participation in the study would be harmful to the participant or the integrity of the study data.

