7.2 Definitions

Adverse Event (AE): Any untoward medical occurrence in a clinical investigation participant who has received a study intervention and that does not necessarily have to have a causal relationship with the study product. An AE can, therefore, be any unfavorable and unintended sign (including an abnormal laboratory finding, for example), symptom, or disease temporally associated with the use of the study product, whether or not considered related to the study product.

Serious Adverse Event (SAE): Any adverse event that results in any of the following outcomes:

- Death
- Life-threatening (immediate risk of death)
- Prolongation of existing hospitalization

- Persistent or significant disability or incapacity
- Important medical events that may not result in death, be life threatening, or require intervention or escalation of care may be considered a serious adverse event when, based upon appropriate medical judgment, they may jeopardize the participant and may require medical or surgical intervention to prevent one of the outcomes listed in this definition. Examples of such medical events include allergic bronchospasm requiring intensive treatment in an emergency room or at home, blood dyscrasias or convulsions that do not result in inpatient hospitalization.

Unexpected Adverse Event (UAE): An adverse reaction, the nature or severity of which is not consistent with the investigator's brochure.

Serious and Unexpected Suspected Adverse Reaction (SUSAR): An adverse reaction, the nature of which is not consistent with the investigator's brochure with severity as defined by SAE above.

Unanticipated Problem (UP): Unanticipated Problem that is not an Adverse Event (e.g. breaches of confidentiality, accidental destruction of study records, or unaccounted-for study drug).

Protocol Deviation: Deviation from the IRB-approved study procedures. Designated serious and non-serious

Serious Protocol Deviation: Protocol deviation that is also an SAE and/or compromises the safety, welfare or rights of participants or others

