8.2 Individual Criteria for Discontinuation

A participant will be closely monitored if AST or ALT > 3 x ULN, and a participant should be removed from disulfiram treatment if AST or ALT > 5 x ULN (DAIDS Grade 3 toxicity).

A participant whose treatment is terminated should remain in the study for appropriate follow up assessments as outlined in section 6.2.

HUMAN PARTICIPANTS

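### Section 8.1's only count-and-grade stopping trigger, (d), covers laboratory toxicity alone, so two matching non-serious Grade 3 clinical events pause dosing only by judgment

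*Combined protocol and SAP*

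**What the plan says.** Section 8.1 does two jobs with one list. It governs the SMC's decision after cohort 1, when the committee must "determine whether it is safe to proceed with enrolling the final cohort using the below criteria", and it sets the events that stop enrollment and dosing for ad hoc review at any time.

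- (a) and (b): death within an hour of dosing, and life-threatening hypersensitivity.
- (c): "One participant with an SAE associated with study product", whatever its grade.
- (d), the only trigger with both a count and a grade: "Two participants with a Grade 3 or higher lab toxicity for the same parameter associated with study product".
- (e): "An overall pattern of symptomatic, clinical, or laboratory events that the SMC considers associated with study product", where the events look minor singly but may be a concern together.
- (f): any other event that the responsible physician considers serious, with no association requirement.

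A general clause before the list also stops the study if "in the judgment of the study physician, participant safety is at risk of being compromised".

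Elsewhere, section 8.2 sets one fixed individual limit, on liver enzymes: "a participant should be removed from disulfiram treatment if AST or ALT > 5 x ULN". Section 7.2 lets important medical events count as serious by judgment; they "may be considered a serious adverse event when, based upon appropriate medical judgment, they may jeopardize the participant". Section 5.3.3 allows withdrawal of an individual "if the investigator determines that continued participation in the study would be harmful to the participant". Grade 3 or higher events found on telephone calls are notified to the principal investigator (sections 5.5.4, 5.5.5 and 5.5.7 to 5.5.9), and the protocol team reviews all adverse events weekly (section 7.4.1).

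**The concern.** Two participants with the same Grade 3 laboratory abnormality force a pause. Two with the same non-serious Grade 3 clinical toxicity do not. Yet the harms that the protocol itself describes as dose-related are mainly clinical: section 4.1.4 names psychotic reactions, hypotension and neuropathy. Section 4.1.8 reports that a study of 2000 mg disulfiram with vorinostat was halted after both recruited patients had confusion, lethargy, ataxia or paranoia. A count of laboratory values would not register such events.

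At stake is how soon dosing pauses at 2000 mg. Table 1 gives a median disulfiram AUC of 22,331 at 2000 mg and 8,386 at 1000 mg, a ratio of 2.66, so a clean first cohort does not settle safety in the second. The dose-linked SMC review takes place before any 2000 mg dose is given, and the synopsis states ongoing committee monitoring for serious events only.

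**Working it through.** **Step 1: classify the triggers in section 8.1.** The section states no operating characteristics, so there is no figure to reproduce. The check is textual.

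| Trigger | Count | Grade | Reaches non-serious clinical events? |
|---|---|---|---|
| (a), (b) | single event | none | No; serious by nature |
| (c) | one | none | No; requires an SAE |
| (d) | two | 3 or higher | No; laboratory only |
| (e) | none | none | Yes, by SMC judgment |
| (f) | none | none | Only if judged serious |
| General clause | none | none | Yes, by study-physician judgment |

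One of the six listed triggers combines a count with a grade, and it excludes clinical events. Section 7.3.3 treats seriousness and severity separately, so a Grade 3 clinical event need not be an SAE.

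**Step 2: how often a parallel clinical rule would matter.** Inputs: n = 20 participants on 2000 mg (section 5.3.4). The total rate p of product-associated Grade 3 or higher events in one category, and the share f of them classed as serious, are assumptions; the documents give neither.

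If all such events were non-serious, the chance of two or more is 1 − (1 − p)^20 − 20p(1 − p)^19:

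- p = 1%: 1.7%
- p = 2%: 6.0%
- p = 5%: 26.4%

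Some events would be classed as serious and would already fire (c). The chance that the extended rule fires while no serious event in that category has occurred is

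(1 − fp)^20 − (1 − p)^20 − 20(1 − f)p(1 − p)^19.

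- p = 2%, f = 0.25: 0.9046 − 0.6676 − 0.2044 = 0.033
- p = 2%, f = 0.50: 0.8179 − 0.6676 − 0.1362 = 0.014
- p = 5%, f = 0.25: 0.7776 − 0.3585 − 0.2830 = 0.136
- p = 5%, f = 0.50: 0.6027 − 0.3585 − 0.1887 = 0.056

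The increment over (c) is thus about 1–3% at a 2% rate and 6–14% at a 5% rate. These figures assume that nobody acts under (e) or the study-physician clause, so they are upper values for the rule's added effect at those rates. They use 20 rather than 30 because applying an active-drug rate to the 10 placebo recipients would overstate the result.

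**The case against.** A reader might infer that repeated Grade 3 clinical events are not a criterion against opening 2000 mg, or that the plan cannot stop for them. The documents do not support either reading. Trigger (e) is on the list that the SMC applies at escalation, it names symptomatic and clinical events, and the committee reviews safety and tolerability data in general at that point. What is missing is a number, not a criterion.

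The contrast between rule and judgment is also only partial. Trigger (d) and any extension require the event to be associated, which section 7.3.4 defines as having no other explanation. Table 3 lists trouble thinking, dizziness, unsteadiness and numbness among the COVID-19 symptoms asked about, so rival explanations will be common. An investigator willing to call two such events drug-related could already pause dosing under the general clause.

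The background evidence is limited too. Section 4.1.4 speaks of serious effects, for which one associated case fires (c). The halted study ran 28 days at 2000 mg with vorinostat, and neither grade nor seriousness is reported, so it does not show that such events would escape (c), (e) or (f). Section 4.1.8 reports no Grade 2–4 events in 30 patients given short-course disulfiram alone across three doses. Further safety endpoints are to be agreed with the committee before the study starts (section 7.4.1) and are not shown.

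All of this stands, and it keeps the point small. It does not explain why the fixed count should apply to laboratory values and not to the kind of toxicity that the protocol names. Zero events in 30 leaves a one-sided 95% upper bound of 1 − 0.05^(1/30), about 10%, and the bound is wider for the unstated number who took 2000 mg.

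**Conclusion.** The gap is real and narrow. By rule, two matching product-associated, non-serious Grade 3 or higher clinical events do not pause dosing; by judgment, they may. That follows from the text and needs no assumed rate.

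The benefit of closing the gap does depend on assumptions. With one event category, independent participants, rates of 2% or 5% and a quarter to a half of events serious, the added rule would act when (c) has not with chance about 1–3% or 6–14% among the 20 on 2000 mg, less whatever judgment would already have caught. It may never be used. The consequence of firing is a pause for SMC review, not termination. This is a low-cost improvement to a plan that already pauses for a single associated SAE, not a defect that leaves clinical toxicity unmonitored.

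**What to change.** Add to trigger (d): *or two participants with the same Grade 3 or higher clinical adverse event (neuropsychiatric events counted as one category) associated with study product*. Leave every other trigger and the general clause as they are. Neuropsychiatric events are pooled because the two cases in section 4.1.8 showed a mix of symptoms that a same-term count could miss.

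Add the DAIDS grade and the two-level association of section 7.3.4 to the adverse event log (Table 4), which now records mild, moderate or severe and five levels of relatedness. The rule can then be applied at the weekly team review. MedDRA coding is planned for analysis (section 6.2.4), but coding in real time is not stated, so the team would assign the category at that review.

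The cost is a short amendment, SMC agreement and a revised log, with no added visits, tests or participants. The downside is an occasional extra pause, sometimes for COVID-19 symptoms wrongly judged associated. Because firing stops dosing, a pause may interrupt the five-day course and affect day-5 primary endpoint data for participants then on treatment. Restricting the rule to the same event, with only neuropsychiatric events pooled, keeps such pauses fewer than a count across broad organ-system categories would.
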